2.0 Objective(s)

2.1 Primary Objective

Use of the powered Empower ankle prosthesis to determine differences in socket pressures compared to both the microprocessor-controlled PROPRIO FOOT® and a user's standard passive prosthesis for level-ground walking, stair ascent, and ramp ascent.

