3.0 Outcome Measures/Endpoints

3.1 Primary Outcome Measures

Determine the effects of a powered transtibial prosthesis on the socket pressure for level-ground walking, stair ascent/descent, and ramp ascent/descent in comparison to a microprocessor-controlled prosthesis and a passive prosthesis at 4 weeks.

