5.0 Study Design

Participants will have the option to choose to attend 4 or 6 study visits. The number of visits participants decide to choose is based on subject preference depending on preferred time allocation. If opting for 4 study visits, visit 3 and 4 will be combined, as well as visit 5 and 6. The total time per participant to complete all visits will remain the same despite which option is chosen.

Randomization: Upon completion of study visit 1/ evaluation the subject will be randomized to initially receive either the PROPRIO FOOT® or the Empower ankle. A licensed prosthetist will fit the subject with the designated device at study visit 2 and establish the control settings per manufacturer recommendations and complete an alignment. The alternate device will be fitted at study visit 4.

Study Visit 1/Evaluation: This initial visit will take place at IU Health Methodist Hospital. Subjects will need to be evaluated to see if they are candidates for a prosthetic foot. They will need to undergo a clinical evaluation prior to determining eligibility, examining limb length and MPT-to-floor measurements. Additionally, for women participants of childbearing potential, attestation is required stating participant is not currently pregnant, nor planning to become pregnant and the date of their last menstrual period. Once subject is deemed to be a candidate, the following research activities will take place.

- Informed consent and HIPAA (if not previously completed)
- Research personnel will administer Socket Comfort Score questionnaire and PEQ-13 survey and CLASS survey
- Body weight recorded.
- Non-invasive limb health measurements performed (TEWL and Laser Speckle Imaging (LSI))
- Randomization
- Licensed prosthetist will perform pre-fitting and adjustments on the patient, ensuring the research foot (Foot A) will be ready to deliver during participant's next visit

Study Visit 2/Baseline: The subject's second visit will take place at the Noyes Pavilion of IU Health Methodist Hospital (Noyes). Study Visit 2 will occur within a week after Visit 1 with a window of 0-7 days. Participants will be asked to wear fitting shorts/athletic wear for visits held at Noyes prior to attending this visit. Study team members will offer specific guidance on style if necessary. The following procedures will be performed during this visit:

- Digital shape capture
- Administer pressure sensors inside participant's standard-of-care socket and initiate recording

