- Body weight recorded.
- Multiple ambulation trials will be performed including level-ground walking tasks, stair ascent/descent tasks, and ramp ascent/descent trials
- 3D motion capture using the motion capture system will be conducted with the use of an electronic device that measures and reports a body's specific force, angular rate, and sometimes the orientation of the body, which are placed on subjects clothing to capture movement
Walking tasks and ascending/descending tasks on stairs and ramps will be completed with the use of force-sensing pads
- Timed get up and go test will be performed: subject will stand from seated position and walk 3 meters and then return and sit down
- Prosthetist will fit the participant with the research foot that was randomized to them
 - 15-30 minutes of usage of the prosthetic foot will be provided for acclimation
- Subject will repeat the level-ground, stair, and ramp trials with the new prosthetic foot (Foot A)
- Prosthetist will remove pressure sensors from the socket after ambulation and recording will be terminated

Upon completion of baseline, the subject will wear the research device (Foot A) for 4 weeks to become accustomed to the new technology through its exclusive use in place of their standard-of-care prosthetic foot.

Study Visit 3: After the four-week acclimation period, the subject will return for Visit 3 at IUH Methodist Hospital. A window of +/- 7 days will be implemented, ensuring the duration to complete Visit 3 remains consistent among all participants. The following activities will take place during Visit 3:

- Participant's weight will be captured
- Research personnel will administer surveys (Socket Comfort Score, CLASS and PEQ-13)
- Non-invasive limb health measurements performed (TEWL and Laser Speckle Imaging (LSI))

- Licensed prosthetist will perform pre-fitting and adjustments on the patient, ensuring the other research foot (Foot B) will be ready to deliver during participant's next visit

Study Visit 4 (Study Visit 3 if opted for 4 Study Visits): Study Visit 4 will occur within a week after Visit 3 with a window of 0-7 days. This visit will take place at Noyes. The following activities will take place:

- Digital shape capture will be performed
- Administer pressure sensors on participant's research socket and recording will be initiated using Foot A
- Body weight recorded.

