6.0 Enrollment/Randomization

Upon completion of Study Visit 1/Evaluation, the subject will be randomized to initially receive either the PROPRIO FOOT® or the Empower ankle. At study visit 4, the subject will switch to the alternate device.

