13.0 Statistical Considerations

This longitudinal study will compare the effects of the three prostheses on the various measured quantities for each subject. Motion capture data will be filtered with an 8 Hz Butterworth low-pass filter, and ground reaction forces will be filtered with a 50 Hz critically damped filter. These data will be collected and analyzed primarily to interpret how differences in kinematics and kinetics associated with the prostheses contribute to corresponding differences in socket pressure and limb health measures. All pressure measurements will be normalized with respect to body weight as measured during the session of data collection. Mean peak pressure within and pressure-time integrals across each gait cycle will be calculated for each sensor location. The peak pressure provides an indication of the maximum loading at any location, while the pressure-time integral combines both the magnitude and duration of loading since both are relevant for limb health.

The 3D scans of the residual limb will be compared between Visits 2 and 4 and between Visits 4 and 6 as a means of interpreting whether significant changes in socket pressure are due to corresponding changes in residual limb volume and/or shape. Both TEWL and skin perfusion, i.e., laser speckle imaging, will be measured or quantified into continuous scales from a three-period, baseline, 30 min post-fitting and 4 weeks post-fitting. The values will be normalized using the values collected from the corresponding reference site [62].

Mean peak socket pressure will serve as the primary outcome measure, with particular emphasis on the proximal region of the anterior surface. Pressure-time integrals will serve as the secondary outcome measure, again emphasizing the same region. TEWL values will be used as the primary outcome measure of overall limb health, while skin perfusion will be the secondary outcome measure. For each measure, comparisons among the three prostheses will be made via a repeated measures ANOVA with Bonferroni correction. For both aims, the survey responses will provide a means of evaluating whether subject impressions aligned with quantitative measures of socket pressure and limb health.

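### Section 13 names no period term and the passive prosthesis is always measured first, so the passive contrasts mix device with change since baseline

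*Combined protocol and SAP*

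**What the plan says.** - **Analysis.** Section 13.0: "For each measure, comparisons among the three prostheses will be made via a repeated measures ANOVA with Bonferroni correction". Prosthesis is the only factor named. The three periods mentioned there for TEWL and skin perfusion are measurement times, not a model term.
- **Target contrasts.** Section 2.1 sets Empower pressures "compared to both the microprocessor-controlled PROPRIO FOOT® and a user's standard passive prosthesis". Section 3.1 asks for the effect "in comparison to a microprocessor-controlled prosthesis and a passive prosthesis at 4 weeks".
- **Randomisation.** Section 6.0: "the subject will be randomized to initially receive either the PROPRIO FOOT® or the Empower ankle". No allocation ratio or blocking is stated.
- **Order of measurement.** Section 5.0 and the Section 8.0 calendar put passive pressure at Visit 2, Week 2 ("Administer pressure sensors inside participant's standard-of-care socket and initiate recording"). The 4-week Foot A pressure is at Visit 4, Week 7 ("Administer pressure sensors on participant's research socket and recording will be initiated using Foot A"), and the 4-week Foot B pressure at Visit 6, Week 12. TEWL and LSI are at Weeks 1 (passive), 6 and 11. Passive is never measured again.
- **Four-visit option.** Section 5.0 lets participants combine Visits 3 and 4, and Visits 5 and 6.
- **Partial controls.** Pressure is normalised to same-session body weight. TEWL and LSI are normalised to a reference site. Limb scans are compared across Visits 2, 4 and 6 for interpretation. Section 4.2 excludes significant persistent limb-volume fluctuation.

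**The concern.** Randomising the order of the two active feet protects only the comparison between them. The passive value is fixed at the first occasion, so change in the limb, the socket fit, the sensor placement or the subject's familiarity with the tasks falls into both passive contrasts. Empower versus passive is half of the primary objective, and mean peak pressure is the primary outcome. A single three-level ANOVA would report this contrast on the same footing as the randomised one, and change since baseline could be read as a device effect. The same model also leaves Empower versus PROPRIO unadjusted for period if the realised orders are unequal.

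**Working it through.** The plan states no sample size, power, SD, alpha or drift, so it has no figure to reproduce.

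**1. Time offsets (Section 8.0).** Pressure: 7 − 2 = 5 and 12 − 2 = 10 weeks after passive. TEWL/LSI: 6 − 1 = 5 and 11 − 1 = 10 weeks. Under the four-visit option the pressure offsets are about 4 and 8 weeks.

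**2. Bias of the ANOVA as written.** Let drift be d per step and shared by all subjects, with passive at step 0, Foot A at step 1 and Foot B at step 2. Let nAB subjects start on Empower and nBA on PROPRIO.
- Empower − passive: d(nAB + 2nBA)/N. With equal orders this is 1.5d.
- PROPRIO − passive: d(2nAB + nBA)/N. With equal orders this is also 1.5d.
- Empower − PROPRIO: d(nBA − nAB)/N. This is zero with equal orders and 0.5d in size at 9:3, since (9 − 3)/12 = 0.5.

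**3. Illustrative error rates.** Assumptions: SD 1 per measurement, equal orders, no true device effect, and a two-sided test at 0.05/3 = 1.7% with pooled residual error. The values of N, the SD and d are assumed. False positives for Empower versus passive by simulation:

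| d per step (SD) | N = 12 | N = 20 |
|---|---|---|
| 0.1 | 2% | 3% |
| 0.25 | 6% | 10% |
| 0.5 | 22% | 43% |
| 1.0 | 76% | 97% |

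The table assumes no extra variance between sessions. At N = 12 and d = 0.5, adding a subject-by-session SD of 0.5 or 1 lowers the 22% to 18% or 11%. With four-visit timing and no session variance it is 14%.

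**4. Adding a session term to three values per subject.** With passive and the two 4-week values only, the design has rank 15 of 16 at N = 12. Empower − PROPRIO can be estimated; neither passive contrast can. This is the position of TEWL and LSI on the calendar.

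**5. Using every battery-on pressure set.** There are five: passive and newly fitted Foot A at Visit 2, 4-week Foot A and newly fitted Foot B at Visit 4, and 4-week Foot B at Visit 6. With subject, session and five condition effects the design has full rank (18 of 18). Empower − passive can then be estimated free of a common drift, with SE √(4.5/12) = 0.61 SD against √(2/12) = 0.41 SD for the simple ANOVA.

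Two checks limit this:
- With one carryover term for newly fitted Foot B at Visit 4, the rank is 18 of 19 and the passive contrasts cannot be estimated.
- Suppose four weeks on either active foot truly shifts pressure by 1 unit and the shift persists when Foot B is fitted. The model returns 0 for both 4-week passive contrasts and puts the shift into the session terms. If only Empower causes the shift, and it carries into newly fitted PROPRIO, the model returns 0.5 for Empower − passive (truth 1) and −0.5 for PROPRIO − passive (truth 0).

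**6. TEWL/LSI 30 minutes after fitting.** Section 13.0 mentions this value; the calendar and the visit lists do not. If it were taken at Visits 2 and 4, it would link passive to the active feet only if Visits 1–2 and Visits 3–4 were each treated as one occasion (rank 18 of 18). Treated as separate occasions, the rank is 18 of 20 and the link fails.

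**7. Price of a period term for Empower − PROPRIO.** Residual degrees of freedom fall from 22 to 21 at N = 12. The SE is multiplied by 1/√(1 − ((nAB − nBA)/N)²): 1.00 at 6:6, 1.06 at 8:4 and 1.15 at 9:3.

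**The case against.** The strongest reply has four parts.

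- **The planned pressure data already answer the question.** A reader might infer this from the same-session pairs at Visits 2 and 4. The documents do not support it. The only link back to passive is Foot B, fitted at Visit 4 after four weeks of exclusive use of Foot A and with 15 to 30 minutes of acclimation. Separation rests on an assumption of no carryover that these five sets cannot test, and the session terms may remove part of the 4-week effect that Section 3.1 asks for. The simple ANOVA keeps such an effect, but mixed with time.
- **No drift is shown.** This is correct. No section gives or implies a size, and at d = 0.1 SD the illustrated error rate barely moves. The plan does allow for change, since it scans the limb to interpret pressure differences, and the sensors come out at the end of each pressure session and are placed again at the next. The scans do not enter the model, and the normalisations are partial controls.
- **Empower versus PROPRIO is randomised.** This stands. Under simple 1:1 randomisation its expected bias is zero, and a split of 9:3 or worse has a probability of about 15% at N = 12. The period term is ordinary crossover practice and not the cure of a serious flaw.
- **Power.** The five-set model has 30% power for a 1.2 SD Empower − passive effect at N = 12 without drift, against 63% for the simple ANOVA. By mean squared error it is better only above √(0.612² − 0.408²)/1.5 = 0.30 SD of drift per step. It therefore cannot replace the main analysis.

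**Conclusion.** The concern holds for the structure of the analysis. As written, both passive contrasts include any change since baseline, with bias 1.5d under equal orders, and nothing in the stated model separates the two. This follows from the visit schedule and the scope of the randomisation, without any assumed number. The 22%, 18% and 11% rest on N = 12, a linear shared drift of 0.5 SD per step and a test at 0.05/3. They should not be read as the error rate of this trial. Nor should a reader conclude that the plan only has to add a session term: for TEWL and LSI on the calendar that leaves the passive contrasts without an estimate, and for pressure it works only without carryover. Empower versus PROPRIO is sound apart from the missing period term and the unstated allocation. This should be fixed before analysis; confidence is medium, because the size of any drift is unknown.

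**What to change.** 1. Name 4-week Empower versus PROPRIO as the randomised comparison. Analyse it with subject, device and period terms, and allocate the two orders 1:1 in blocks. The cost is one residual degree of freedom, plus the SE factors in step 7 of the working if the orders end up unequal.
2. For pressure as well as TEWL and LSI, report the passive contrasts as non-randomised before-after differences that mix device and time. Do not present them as pure device effects. This costs only wording.
3. Optionally, for pressure, add a sensitivity analysis of all five battery-on trial sets with session effects and a random subject-by-session term. State that it separates device from time only without carryover into newly fitted Foot B at Visit 4, that its session terms can absorb a real and persistent effect of wearing an active foot, and that its SE is larger (0.61 against 0.41 SD at N = 12).
4. Reconcile the TEWL/LSI value taken 30 minutes after fitting in Section 13.0 with Sections 5.0 and 8.0, which do not list it. Say whether it is collected and at which visit.

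None of this needs a new visit, trial or measurement.

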2.2 Secondary Objective

Obtaining quantitative measures of limb health, transepidermal water loss (TEWL) and skin perfusion, to identify differences among the use of the Empower ankle, the PROPRIO FOOT®, and an individual's standard passive prosthesis.

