3.2 Secondary Outcome Measures

Determine the relative impact on residual limb health of the use of a powered prosthesis, a microprocessor-controlled prosthesis, and a passive prosthesis for individuals with transtibial amputation at 4 weeks.

- Transepidermal water loss (TEWL) measurements at 4 weeks
- Skin perfusion measurements and analysis at 4 weeks
- PEQ, CLASS and Comfort Score responses at 4 weeks

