11.0 Safety Monitoring Plan

A physician who is a member of the study team and the study coordinator will meet at the following timepoints to review the study data and any adverse events to ensure continued subject safety: prior to initiation of the study, after the 5th subject is enrolled, after the 10th subject is enrolled, and 60 days following the conclusion of study procedures for all subjects.

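### For limb health, single-step Bonferroni over three foot pairs is valid but less efficient than a step-down test with the same family-wise bound

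*Combined protocol and SAP*

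**What the plan says.** The secondary objective (2.2) is to measure limb health "to identify differences among the use of the Empower ankle, the PROPRIO FOOT®, and an individual's standard passive prosthesis". Section 3.2 words the outcome the same way, with 4 weeks as the time point: "Determine the relative impact on residual limb health of the use of a powered prosthesis, a microprocessor-controlled prosthesis, and a passive prosthesis". Neither names a reference foot, so the three pairs (powered v microprocessor, powered v passive, microprocessor v passive) are all in question.

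The socket-pressure objective (2.1) is framed differently. It sets the Empower against each of the other two, "to determine differences in socket pressures compared to both the microprocessor-controlled PROPRIO FOOT® and a user's standard passive prosthesis", which is two contrasts.

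Section 13.0 ranks the limb-health measures: "TEWL values will be used as the primary outcome measure of overall limb health, while skin perfusion will be the secondary outcome measure". It gives one analysis rule for every measure: "For each measure, comparisons among the three prostheses will be made via a repeated measures ANOVA with Bonferroni correction". It does not state alpha, sidedness, the divisor or the comparisons that form the family, and it plans no simultaneous confidence intervals. It also says that TEWL and perfusion values come "from a three-period, baseline, 30 min post-fitting and 4 weeks post-fitting", so the family could be read as covering more than one time point. No sample size is given. The only hint is in section 11.0, where safety reviews fall "after the 5th subject is enrolled, after the 10th subject is enrolled".

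**The concern.** With no step-down or closed procedure named, the plain reading of "a repeated measures ANOVA with Bonferroni correction" is that all three pairs are held to 0.0167 whatever the other tests show. With exactly three means this is stricter than family-wise control requires. Once one pair is known to differ, the other two cannot both be equal, so at most one true null is left to protect.

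What is at stake is the second and third comparison. A statement that one foot differs from both others needs two rejections, and a full ranking of the feet needs three. If the trial is small, as the safety-review schedule allows but does not establish, those later rejections are the ones most easily missed.

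**Working it through.** **Inputs.** From the documents: three feet, three pairs and a Bonferroni correction (2.2, 3.2, 13.0). Assumed because not stated: two-sided family-wise alpha 0.05, divisor 3, n from 12 to 30, standardised paired differences from 0.5 to 1.6, and paired t tests. The plan has no power figure to reproduce.

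**Thresholds, smallest p-value first.**
- Bonferroni: 0.0167, 0.0167, 0.0167.
- Holm: 0.05/3 = 0.0167, then 0.05/2 = 0.025, then 0.05, stopping at the first failure.
- Shaffer for three means: 0.0167 and, if rejected, each of the other two at 0.05.

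**Why Shaffer controls the error.**
1. All three pairs equal: a false rejection needs the smallest p to be at or below 0.05/3, which has probability at most 3 × 0.05/3 = 0.05.
2. Exactly two pairs equal: impossible, since A = B and B = C force A = C.
3. Exactly one pair equal: only one false rejection is possible, and that pair is never tested above 0.05.
4. No pair equal: no false rejection is possible.

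The argument needs valid pairwise tests at one time point. It does not use the ANOVA F-test.

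**Why it never does worse.** If Bonferroni rejects anything, the smallest p is at or below 0.0167, so the step-down gate opens. Every pair that Bonferroni rejects then meets its step-down threshold. Both rules share that first condition, so the chance of at least one rejection is identical: 69% under each at n=12 in the setting below.

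**Size, by simulation.** At least 40,000 trials per setting, three conditions, paired-difference SD 1, one foot differing from both others by 0.8.

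| n | Power per true contrast: Bonferroni / Holm / Shaffer | Power for both true contrasts: Bonferroni / Holm / Shaffer |
|---|---|---|
| 12 | 51% / 55% / 60–61% | 33% / 41% / 52% |
| 16 | 69% / 73% / 78% | 54% / 62% / 72% |
| 20 | 82% / 85% / 89% | 71% / 78% / 85% |

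For both contrasts, Shaffer gains 52 − 33 = 19, 72 − 54 = 18 and 85 − 71 = 14 points. Holm gains 41 − 33 = 8, 62 − 54 = 8 and 78 − 71 = 7.

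**Error.** With all feet equal, family-wise error at n=12 is about 4.5% for Bonferroni and for Shaffer. In the setting of the table, error on the truly equal third pair at n=12 rises from 1.7% (Bonferroni) to 4.6% (Shaffer). At n=20 it rises from 1.65% to 4.91%.

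**Sensitivity to the assumptions.**
- Equally spaced means, adjacent difference 0.8, n=15: power for all three pairs is 37.6% (Bonferroni), 64.4% (Holm) and 65.4% (Shaffer).
- One foot differing by 0.8, n=30: both contrasts 93.0%, 95.5% and 97.6%.
- One foot differing by 1.2, n=20: per contrast 99.5% (Bonferroni) to 99.9% (Shaffer).
- One foot differing by 0.5, n=12: per contrast 19% (Bonferroni) to 23% (Shaffer).
- Pooled ANOVA error under sphericity, difference 0.8, n=12: Bonferroni alone reaches 58% per contrast and 43% for both, against 51% and 33% with separate paired t tests.

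**The case against.** **Bonferroni is a valid method, and these are secondary measures.** This stands. No result under the plan would be wrong on this account. A reader might infer that the plan contains an error; it does not. The point is one of efficiency.

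**The gain is not free.** A reader might infer that Bonferroni loses power for no return. That goes too far. Bonferroni comes with simultaneous intervals that match its tests, and its realised error on a truly equal third pair is about a third of Shaffer's. The plan asks for no such intervals and the higher error stays within 0.05, so the trade is reasonable, but it is still a trade.

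**One foot against both others is not the stated target.** This also stands. Objective 2.2 asks only about differences among the feet. A reader might further infer that this pattern is where the loss is greatest. The figures say otherwise: at n=15 the gap for complete detection is 65.4 − 37.6 = 27.8 points with equally spaced means, larger than the 14 to 19 points seen for n=12 to 20 when one foot stands apart.

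**The size is assumed.** Correct. The documents fix no n, alpha, SD or effect, and the planned ANOVA might use pooled error, which starts from higher power. The ordering of the rules follows from logic; the percentages are illustrations.

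**The undefined family is the more basic gap.** This is fair. If the correction spanned three pairs at three time points, the divisor would be 9 and the threshold 0.05/9 = 0.0056. The three-mean argument applies only to three pairs at one time point, so any step-down sentence must name that time point.

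**Conclusion.** The point holds as an inexpensive improvement. For TEWL and for perfusion all three pairs are in question, and single-step Bonferroni is dominated by Shaffer's rule under the same 0.05 family-wise bound. Under the assumed 0.8 SD with one foot apart, Shaffer adds 14 to 19 points of power to show both true contrasts for n from 12 to 20, and Holm adds 7 or 8. The gain is confined to the second and third rejections. Per contrast, it is small when power is already very high or very low. These sizes rest on the assumed n, effect, alpha, divisor and paired t tests.

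A reader might extend this to socket pressure because section 13.0 uses one rule for every measure. The documents do not support that: objective 2.1 poses two contrasts against the Empower, and the three-pair argument was not made for that family.

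**What to change.** In section 13.0, for TEWL and separately for perfusion, replace the bare reference to Bonferroni with text such as: the family is the three pairwise foot comparisons at 4 weeks, with two-sided family-wise alpha 0.05; the smallest of the three p-values is tested at 0.05/3 and, if it is rejected, each of the other two is tested at 0.05 (Shaffer step-down). Holm is an acceptable simpler choice with a smaller gain: roughly half of Shaffer's or less when one foot stands apart, and close to it when the means are equally spaced. State also whether pairs are tested by separate paired t tests or with pooled ANOVA error. The study calendar's only TEWL and perfusion reading on the passive foot is at Visit 1, so say that this is the value compared with the 4-week readings.

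The cost is one or two sentences, with no added subjects, visits or measurements. Intervals will no longer match the tests exactly, so report Bonferroni or unadjusted intervals alongside and label them as such. Accept openly that error on a truly equal third pair rises from about 0.017 to just under 0.05. Make the change before the limb-health data are analysed.

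### For socket pressure, the three-device Bonferroni correction is wider than the two Empower comparisons in the primary objective; Holm over those two would recover power cheaply

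*Combined protocol and SAP*

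**What the plan says.** Section 2.1 sets the primary question as Empower's socket pressures "compared to both the microprocessor-controlled PROPRIO FOOT® and a user's standard passive prosthesis". Section 3.1 repeats it for the powered device, "in comparison to a microprocessor-controlled prosthesis and a passive prosthesis at 4 weeks". Both name two contrasts, and neither asks how PROPRIO FOOT compares with the passive foot on pressure.

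Section 2.2, on transepidermal water loss (TEWL) and skin perfusion, is worded differently. It aims "to identify differences among the use of the Empower ankle, the PROPRIO FOOT®, and an individual's standard passive prosthesis", which covers all three pairs.

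Section 13.0 makes mean peak socket pressure the primary outcome, with emphasis on the proximal anterior region. It then gives one rule for everything: "comparisons among the three prostheses will be made via a repeated measures ANOVA with Bonferroni correction". It does not state the Bonferroni divisor, alpha, the list of pairs, the error term for the contrasts, whether pairwise tests depend on a significant ANOVA, or whether the correction also covers walking tasks and sensor regions. No sample size, effect size or power appears anywhere.

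**The concern.** The analysis rule does not distinguish the two-contrast pressure question from the three-contrast limb-health question. If the correction runs over all three pairs, the two Empower contrasts on pressure share alpha with a comparison that the primary objective does not pose. Single-step Bonferroni is also never more powerful than Holm on the same tests at the same familywise error. What is at stake is the chance of detecting an Empower difference in the primary outcome. The validity of the result is not in question.

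**Working it through.** The plan states no figure that could be reproduced. The inputs are therefore:

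- From the documents: two contrasts for pressure (Sections 2.1 and 3.1), three for limb health (Section 2.2), and repeated measures ANOVA with Bonferroni (Section 13.0).
- Inferred: a divisor of three, the natural reading of a comparison among three prostheses.
- Assumed: two-sided familywise alpha 0.05; N = 10, 15 or 20; standardised paired difference dz = 0.8 (mean difference over the SD of the within-subject difference); equal, independent within-device errors, so sphericity holds; one walking task and one region; no ANOVA gate.

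**Step 1: alpha per contrast.** Three pairs: 0.05/3 = 0.0167 (critical z 2.394). Two contrasts: 0.05/2 = 0.0250 (critical z 2.241). For 80% power, with z = 0.842, the normal-approximation sample-size ratio is ((2.394 + 0.842)/(2.241 + 0.842))² = 1.10. Dividing by three rather than two therefore needs about 10% more subjects.

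**Step 2: power of the plan as read.** With pooled ANOVA error the contrast has df = (3 − 1)(N − 1) = 2(N − 1) and noncentrality dz·√N. Power is P(|T| > t₁₋ₐ/₂) for noncentral T, with a = 0.05/3.

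- N = 10: df 18, noncentrality 2.53, critical t 2.639, power 47%.
- N = 15: df 28, noncentrality 3.10, critical t 2.546, power 71%.
- N = 20: df 38, noncentrality 3.58, critical t 2.505, power 85%.

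**Step 3: Holm over the two Empower contrasts, same pooled error.** The smaller p-value is compared with 0.025 and, if that succeeds, the larger with 0.05. In the both-real case Empower differs by dz = 0.8 from two devices that are equal to each other. In the one-real case Empower equals one comparator and differs by 0.8 from the other. The Holm and joint figures are simulated and are good to about one percentage point.

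| | N = 10 | N = 15 | N = 20 |
|---|---|---|---|
| Bonferroni over three, per contrast | 47% | 71% | 85% |
| Holm over two, per contrast, both real | 60% | 82% | 92% |
| Holm over two, the real contrast, only one real | 55% | 77% | 89% |
| Both significant, Bonferroni over three | 32% | 58% | 77% |
| Both significant, Holm over two | 51% | 75% | 89% |

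The gains are 13/11/7 points per contrast if both are real, 8/6/4 if only one is, and 19/17/12 for both being significant.

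**Step 4: why the error term is held fixed.** With separate paired t-tests (df = N − 1), power at 0.05/3 is 40/65/82% and at 0.05/2 is 47/72/86%. Pooled error at 0.05/3 already gives 47/71/85%. Comparing separate tests before and after would understate the planned analysis. Moving to separate standard errors at the same time as dropping the third pair would give back almost all of the gain from the divisor.

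**The case against.** Bonferroni over three pairs is valid and conservative, so nothing in the plan is wrong or biased. Section 13.0 says that the study compares all three prostheses, and using one family for all measures is defensible. This stands, and it makes the point an efficiency improvement rather than the correction of an error.

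A reader might infer more, and four such readings are not supported:

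- That the third pair costs alpha for nothing. Section 2.2 needs PROPRIO FOOT versus passive for TEWL and perfusion. The argument applies to pressure only.
- That the plan specifies 0.05/3 after an omnibus test. It gives no divisor, alpha or gating rule. If two contrasts were intended, the plan still needs a sentence saying so.
- That the trial is known to be small. The safety review set for "after the 10th subject is enrolled" shows that at least ten subjects are expected. It gives no sample size.
- That testing each contrast with its own paired standard error adds to the gain. Under sphericity it costs degrees of freedom. If only one contrast is real, Holm with separate errors gives 48/72/87% against 47/71/85% for the plan as read, which is almost no gain. Separate errors may be worth having for robustness to non-sphericity, but that is a separate decision.

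Two further objections have force. First, two contrasts are not yet the whole family: Section 2.1 names three walking tasks and Section 3.1 names five, which makes 2 × 3 = 6 or 2 × 5 = 10 tests even in one region. Holm over two controls error within a task only. Second, Holm is not the only remedy. With three devices and sphericity, unadjusted pairwise tests after a significant ANOVA at 0.05 held simulated familywise error at 0.049 to 0.051. That route depends on sphericity, and the plan does not specify it.

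**Conclusion.** The point holds as a cheap improvement for the primary pressure outcome. The objective and the primary outcome name two contrasts, while the analysis rule most naturally covers three. With the error term unchanged, Holm over the two is never less powerful than Bonferroni over three for the Empower contrasts, and within a task it keeps familywise error at or below 0.05. That ordering does not depend on N or effect size; the size of the gain does. Under the assumptions above it is 4 to 13 points per contrast and 12 to 19 points for both being significant, and it shrinks as N grows. None of these magnitudes can be derived from the documents alone.

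**What to change.** In Section 13.0, before any outcome data are examined:

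1. For mean peak pressure in the proximal anterior region, name Empower minus PROPRIO FOOT and Empower minus passive as the confirmatory contrasts. Test them with Holm at two-sided familywise 0.05 in place of single-step Bonferroni.
2. State whether the 0.05 holds within each walking task or whether the family also spans the tasks, and reconcile the three tasks of Section 2.1 with the five of Section 3.1.
3. Report PROPRIO FOOT versus passive on pressure as supportive.
4. Keep all three pairs for TEWL and perfusion. Holm can replace Bonferroni there too.

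The choice between pooled ANOVA error and contrast-specific standard errors should be made and stated separately, on robustness grounds.

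The cost is a few sentences in Section 13.0, with no extra subjects, visits or measurements. The one real loss is that PROPRIO FOOT versus passive is no longer a confirmatory comparison for pressure.
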